Cigar use exposes youth to addictive effects of nicotine during a critical developmental period and increases the risk of multiple cancers and premature death (National Cancer Institute, 1998; Chang et al., 2015). Recent data indicate that cigars are the second most commonly used combustible tobacco product by youth and that past 30-day cigar use is 1.8%, which translates into 280,000 high school students (Birdsey et al., 2023). Of the three major types of cigars—large cigars, little cigars, and cigarillos—little cigars and cigarillos (LCCs) are the most commonly used in the US, particularly among younger people (Wang, 2019). LCC use also contributes to tobacco health disparities, as Black or African American youth use cigars more frequently than other youth (Wang, 2019). In 2016, the Food and Drug Administration (FDA) deemed LCCs subject to FDA regulation, requiring six rotating text-only warning statements to be on LCC packaging (Food and Drug Administration, 2016). Little research has examined the effectiveness of LCC warnings in reducing youth willingness to use LCCs.

Research from studies of *cigarette* warnings suggests that effective LCC warnings should employ images that illustrate negative health effects associated with use and a larger warning label prominently displayed on the pack (Noar et al., 2016; Hammond, 2011). Among youth, health warnings on *cigarette* packs that contain both text statements and images (i.e., pictorial warnings) are more effective (Noar et al., 2016; Hammond, 2011; Hammond et al., 2012; White et al., 2008; Vardavas et al., 2009; White et al., 2015; Peterson et al., 2010; Andrews et al., 2016) and engaging (Hammond, 2011; White et al., 2008; White et al., 2015; Peterson et al., 2010) than text-only warnings. However, evidence for cigarette warning labels cannot adequately inform implementation of improved LCC warnings for three reasons: 1) there is no evidence on the effectiveness of the FDA-mandated text-only LCC warnings on behavioral intentions or other outcomes among youth (Richardson et al., 2013; Sterling et al., 2013; Glasser et al., 2017), 2) courts have ruled that effective tobacco warnings on one type of tobacco product (i.e., for cigarettes) cannot be used to justify warnings on other types of tobacco (i.e., for LCCs) (R.J. Reynolds Tobacco Co. et Al. v. U.S. Food and Drug Administration, 2012), and 3) LCC users have different demographic and consumption profiles than cigarette users (i.e., LCC users are younger (Substance Abuse and Mental Health Services Administration, 2017), include more Black/African Americans (Substance Abuse and Mental Health Services Administration, 2017), and use LCCs on fewer days per month (Nyman et al., 2016; Jamal et al., 2018)). Furthermore, on July 7, 2020, the US Court of Appeals for the DC Circuit ruled that the FDA cannot require their new warning labels for cigars, claiming that the FDA did not provide evidence on the impact of cigar warnings on smoking rates, including initiation and cessation (*Cigar Association of America v. United States Food and Drug Administration*, 2020).

Objectives

Our goal is to conduct research that advances the science on LCC warnings that are effective for youth who currently use, have ever used, or are susceptible to using LCCs. This study will inform FDA implementation of LCC warnings, which can reduce LCC use and lessen tobacco health disparities among youth.

Hypotheses

- We hypothesize that LCC warnings at 30% size that include an image (i.e., pictorial warnings) will decrease willingness to use LCCs, compared with FDA-proposed text-only LCC warnings at 30% size and Surgeon General text-only warnings at 10% size.
- We hypothesize that LCC warnings at 30% size that include an image (i.e., pictorial warnings) will increase cognitive elaboration, knowledge of LCC harms, beliefs about LCC harms, and negative affect compared with FDA-proposed text-only LCC warnings at 30% size and Surgeon General text-only warnings at 10% size.
- We hypothesize that LCC warnings at 30% size that include an image (i.e., pictorial warnings) will decrease LCC susceptibility, past 7 day little cigar use, and past 7 day cigarillo use compared with FDA-proposed text-only LCC warnings at 30% size and Surgeon General text-only warnings at 10% size.

Trial Design

The study is designed to be a parallel group trial, with participants evenly allocated to each study condition, using a superiority framework.

Methods: Participants, Interventions, and Outcomes

Methods Overview

We will conduct a one-week web-based RCT among U.S. youth who are susceptible to, have ever used, or currently use LCCs. In this study, LCC warnings on packs will be electronically presented to participants daily to determine if pictorial LCC warnings at 30% size decrease willingness to use LCCs compared to FDA proposed text-only warnings at 30% size and a control condition (Surgeon General text-only warnings at 10% size). We will apply a daily diary methodology to present LCC warnings on packs to participants over time. Qualtrics will contact, screen, consent and administer the survey. To enroll participants, Qualtrics will screen participants using our inclusion criteria and measures and invite eligible participants to enroll in the study. To collect at least 700 quality completes, we anticipate enrolling up to 2,100 people.

At the beginning of the baseline survey (day 1), participants will first consent to participate in the study and then complete a questionnaire about their LCC use and susceptibility, exposure to cigar advertising and warnings, and demographic characteristics, in addition to other measures. At the end of the baseline questionnaire, survey software will randomly assign participants to one of the 3 study conditions. The three study conditions are 1) Pictorial (text + image) 30% size warnings , 2) FDA-proposed text-only LCC warnings at 30% size, and 3) Control condition (current status Surgeon General text-only warnings at 10% size). Participants will be contacted each day and invited to complete the survey for that day of the study protocol.

For six subsequent days (days 2-7), participants will be contacted and asked to complete a daily survey. During these daily surveys, participants will view an image of a cigarillo package with a warning according to the participant's condition. Participants will view a total of 6 different warnings over the course of 6 days. Before seeing the warning, participants will be asked about how often they have thought about the health risks of smoking cigars. After seeing the warning, participants will be asked about the appeal of the cigars in the package, how relevant they feel the warning is to their lives, and how worried the warning makes them feel. Participants will also be asked whether they saw any warnings outside the study about the harms of cigar use in the past day.

For the post-test on day 8, participants will be asked to complete a questionnaire about their willingness to use LCCs, LCC use, and susceptibility among other measures.

Participant timeline

Potential participants will be invited to complete the screener (Day 0) and those who are eligible will be invited to participate in the study. On Day 1, eligible participants will be asked to complete a baseline survey. The baseline survey will be open to enrollment for 2 days. After the baseline closes, participants will receive a survey every morning for Days 2-7 that includes an LCC warning and questions about their cognitive elaboration over the previous day, reactions to the warning, and warning exposure over the previous day. Participants will also be asked to complete a final post-test survey on Day 8.

Survey timing:

Study Setting

The study will be conducted with online surveys, so participants can complete the surveys from any location. Participants must reside in the United States (US) to meet eligibility criteria.

Participants

Eligibility criteria for participation in this study:

1. Members of the recruitment panel (we are partnering with a panel provider for recruitment of all participants)
2. Agree to provide their honest answers
3. Susceptible to using LCCs, or have ever used little cigars and/or cigarillos, or currently use little cigar and/or cigarillos in the past 30 days
4. Age 15 – 20 years old
5. Currently living in US or a US territory
6. Inclusion criteria based on the design of the study:
 - a. Able to complete 2 surveys that take approximately 10 minutes
 - b. Able to complete a 2-minute survey each day for 6 days
7. Inclusion criteria based on verifying real participants:
 - a. Able to verify they are not a bot using CAPTCHA
 - b. Able to answer a simple, random math question

Interventions

Experimental Conditions

- 1) FDA-proposed warnings with added images at 30% size (pictorial warnings)
- 2) FDA-proposed text-only LCC warnings at 30% size
- 3) Control condition – Surgeon General text-only warnings at 10% size

Warning Stimuli

The stimuli will vary based on the day of the protocol. The packages that the study warning labels will be shown on will be standardized across the three conditions (see table below for warning text). Specifically, warning labels will be shown on cigarillo packages that are red and branded with the fictitious name “Grey Fox” to minimize the influence of brand loyalty and pre-existing brand perceptions.

Stimuli Order

Day	Condition 1	Condition 2	Condition 3
Day 2	WARNING: Tobacco use increases the risk of infertility, stillbirth and low birth weight.	WARNING: Tobacco use increases the risk of infertility, stillbirth and low birth weight.	SURGEON GENERAL WARNING: Tobacco Use Increases The Risk Of Infertility, Stillbirth And Low Birth Weight.
Day 3	WARNING: This product contains nicotine. Nicotine is an addictive chemical.	WARNING: This product contains nicotine. Nicotine is an addictive chemical.	SURGEON GENERAL WARNING: This Product Contains Nicotine. Nicotine Is An Addictive Chemical.
Day 4	WARNING: Cigar smoking can cause cancers of the mouth and throat, even if you do not inhale.	WARNING: Cigar smoking can cause cancers of the mouth and throat, even if you do not inhale.	SURGEON GENERAL WARNING: Cigar Smoking Can Cause Cancers Of The Mouth And Throat, Even If You Do Not Inhale.
Day 5	WARNING: Cigars are not a safe alternative to cigarettes.	WARNING: Cigars are not a safe alternative to cigarettes.	SURGEON GENERAL WARNING: Cigars Are Not A Safe Alternative To Cigarettes.
Day 6	WARNING: Cigar smoking can cause lung cancer and heart disease.	WARNING: Cigar smoking can cause lung cancer and heart disease.	SURGEON GENERAL WARNING: Cigar Smoking Can Cause Lung Cancer And Heart Disease.
Day 7	WARNING: Tobacco smoke increases the risk of lung cancer and heart disease, even in nonsmokers.	WARNING: Tobacco smoke increases the risk of lung cancer and heart disease, even in nonsmokers.	SURGEON GENERAL WARNING: Tobacco Smoke Increases The Risk Of Lung Cancer And Heart Disease, Even In Nonsmokers.

Additional intervention details

Participants can withdraw from the study at any time if they choose to do so by no longer responding to the survey links and may withdraw their data by contacting the UNC study team.

Multiple strategies have been implemented to maximize adherence to the trial protocol, including reaching out to participants with invitations and reminders each day.

There is no relevant concomitant care or interventions that are permitted or prohibited during the trial.

Outcomes

Primary

- Willingness to use LCCs (day 8)

- Average willingness to use score measured by survey, measured with 2 questions. The final willingness to use score is a mean of the response to the 2 questions, on a scale of 1 to 5, where 1 indicates low willingness to use LCCs and 5 indicates a high willingness to use LCCs.

Secondary

- Past 7 day little cigar use (day 8)
 - Measured by survey with 1 item
- Past 7 day cigarillo use (day 8)
 - Measured by survey with 1 item
- LCC susceptibility (day 8)
 - Measured by survey with 3 items
- Cognitive elaboration about risk of LCC use (day 8)
 - Measured by survey with 1 item
- Warning negative affect/worry (each day)
 - Measured by survey with 1 item
- Knowledge of LCC harms (day 8)
 - Measured by survey with 13 items
- Beliefs about LCC harms (day 8)
 - Measured by survey with 10 items

Other

- LCC quit intentions (day 8)
 - Measured by survey with 3 items
- Past 7 day use of other tobacco products (day 8)
 - Measured by survey with 1 item
- Past 7 day butting out of LCCs (day 8)
 - Measured by survey with 1 item
- Past 7 day forgoing LCCs (day 8)
 - Measured by survey with 1 item
- LCC self efficacy to quit (day 8)
 - Measured by survey with 1 item
- Past 7 day use of blunts (day 8)
 - Measured by survey with 1 item
- Reactance to warnings (day 8)
 - Measured by survey with 3 items
- Conversations about cigar health risks (day 8)
 - Measured by survey with 1 item
- Cigar appeal (each day)
 - Measured by survey with 1 item
- Warning relevance (each day)
 - Measured by survey with 1 item
- Unaided recall of cigar warnings (day 8)
 - Measured by survey with 1 item
- Confirmed recall of cigar warnings (day 8)
 - Measured by survey
- Recognition of cigar warnings (day 8)
 - Measured by survey with 6 items
- Self-reported learning (day 8)
 - Measured by survey with 1 item

Sample Size

The sample size is based on a meta-analysis that compared text-only cigarette warnings to warnings with text and images and reported a standardized mean difference in willingness of $d=0.26$ (Noar, 2016). Based on the standardized effect size observed in that study and enrolling 700 people in the study (233 per group), we would have 80% power at $\alpha=0.05$ to detect the same standardized effect size change between the FDA pictorial warning and FDA text only warning group. Secondary outcomes that are measured daily will have higher power to detect differences between groups.

Recruitment

We are working with Qualtrics research services to conduct this study and enroll participants from one of the panel providers that they work with. Qualtrics has access to high quality research panels across the US. Qualtrics is able to leverage its panels to provide timely and reliable data collection to UNC and other research universities. We have high confidence that Qualtrics will be able to meet our recruitment goals.

Compensation Plan

Qualtrics will manage participant incentives. Participants in studies conducted by Qualtrics receive an incentive based on the length of the survey and their specific profile. The types of rewards vary and may include cash, airline miles, gift cards, redeemable points, sweepstakes entrance and vouchers. For this study, participants who complete the baseline, 3 of the daily message surveys, and the post survey on day 8 will receive an incentive. Participants who complete only a few of the surveys but do not satisfy the criteria above will not receive an incentive.

Methods: Assignment of interventions

Allocation and Blinding

Participants will not be informed specifically about the possible interventions that they may be assigned to. Researchers will not be blinded to the condition that participants have been assigned to. All outcome measures will be assessed via online survey. At the end of the baseline survey, survey software will randomly assign participants to one of the three study arms. Participants will have an equal chance of being randomized to each study arm.

Methods: Data collection management, and analysis

Data collection methods

Data collection will be conducted using Qualtrics web survey platform. Where possible, the measures used are previously developed and validated measures. Multiple strategies have been implemented to maximize adherence to the trial protocol, including reaching out to participants with invitations and reminders each day, and compensating them based on completion of the most important questionnaires (i.e., baseline, at least 3 daily surveys, and the post survey).

Screener

Qualtrics will invite potential participants to complete the screening survey and people who are eligible will be invited to complete the baseline survey. The screener is used to assess participant eligibility and collect demographic data.

Baseline Survey: Day 1

- Eligible participants will be invited to participate in the study and complete the baseline survey to enroll. The baseline survey will be open to enrollment for 2 days.
- The first part of the baseline survey will be an assent/consent form with an agreement to participate in the study.

- The baseline survey contains baseline tobacco use and susceptibility questions and additional demographic questions.
- At the end of the baseline questionnaire, survey software will randomly assign participants to one of the 3 study conditions.

Daily Surveys: Days 2-7

- There are 6 daily surveys, which align with each participant's condition. Participants will stay in their condition throughout the study. Depending on the day, participants will see a different message and be asked questions about their perceptions of the warning and the previous day.

Post Survey: Day 8

- For the post-test on day 8, participants will be asked to complete a questionnaire that is approximately 15 minutes in length about their willingness to use LCCs, susceptibility to LCCs, cigar knowledge, and other relevant survey questions.
- Participants will also be asked about their study experience.

Data Management

Data management will be conducted by the study team. Multiple processes will be implemented to ensure high data quality, including internal pilots to test the protocol and ensure that data collection instruments are working properly, and ongoing data monitoring will be conducted during data collection to ensure that any issues with data quality are caught early and fixed. A pilot of the protocol with actual participants will be conducted before the full study is launched and participants will be asked about their experience in the study at the end of the pilot to further ensure that the protocol is working as intended and ensure high quality data collection.

Statistical Methods

We will analyze the data using intention-to-treat analyses. Our primary outcome is willingness to use LCCs at post-test. We will model willingness to use LCCs with randomly assigned experimental condition as the between-participant predictor.

Analysis methods will depend on the time point that the outcome was measured. Post-test measures will be analyzed differently than repeated measures from the daily surveys, as outlined below.

Analysis methods for post-test measures will use linear models for continuous outcomes, including the primary outcome of willingness to use, and logistic models for dichotomous outcomes. Participants who were randomized to an intervention will be included in the analysis. Missingness will be accounted for by including covariates in regression models where the covariates are assumed to satisfy a missing at random (MAR) assumption for the outcomes. Estimation will proceed using maximum likelihood.

Mixed models will examine differences between treatment groups for items measured multiple times in the daily surveys (e.g., negative affect). For these models, we will use linear mixed modeling to account for the repeated measure design.

Methods: Monitoring

To ensure maximum protection of human subjects, we submitted our research project information to the School of Medicine Data Safety and Monitoring Board at the University of North Carolina at Chapel Hill and asked them to make the final decision regarding risk to participants and whether our study should receive their supervision. A representative of the board agreed that given that the study involves a low risk behavioral intervention in a healthy population, oversight by the board was not necessary.

Adverse events are not expected in this trial due to the minimal risks to participants, and no threat to participant health. Accordingly, plans for collecting, assessing and reporting adverse events are not necessary.

We have no plans for auditing trial conduct.

Ethics and dissemination

This trial was approved by UNC's IRB under IRB # 23-2455.

All protocol changes will be communicated to the study team, and any change in participant interaction will be approved by UNC's IRB. Protocol changes will be tracked in an appendix table with new versions after initial approval including the date, version number, and a summary of changes.

Consent

Consent will be collected electronically as part of the baseline survey at the beginning of the study. At the beginning of the baseline survey, potential participants who are 18 years old or older will view the consent form with an agreement to participate in the study. For participants who are younger than 18, we will collect consent from their parent or guardian and then collect assent from the potential participants themselves. Participants will only be able to proceed with the study with appropriate consent/assent agreements.

Confidentiality

We will take the following steps to minimize the risk to a breach of confidentiality via unauthorized access, use, disclosure, modification, loss or theft of participants' information:

- We will use and enforce appropriate security measures including physical, technical and administrative safeguards.
- Data will be stored on a university secure server that is password accessed and is only accessible to key research personnel.
- All study personnel are required to have valid training on ethics of research on human subjects and to complete confidentiality certification procedures upon employment.
- The research team will not collect nor have access to personal identifying information.

This study proposes research that has been determined to include Security Level 2 data security requirements. The MPIs have agreed to accept responsibility for managing these risks appropriately in consultation with departmental and/or campus security personnel. The Data Security Requirements addendum can be reviewed here:

<https://guides.lib.unc.edu/datasecurity/irbis>

Declaration of Interests

The study team declares that they have no competing interests.

Access to data

On reasonable request, we will make deidentified data sets available, stripped of individual identifiers, following publication of the relevant study's main findings. We may submit deidentified data collected in this study to a data repository, such as UNC Odum Institute's Dataverse (<https://dataverse.unc.edu/dataverse/unc>) to make our deidentified data publicly available. As part of submitting the data to a repository, we will provide basic information about how the data was collected and upload a deidentified dataset to the repository.

Ancillary and post-trial care

This trial presents no more than minimal risk to participants, does not collect data on harms to participants or assess interim data during the trial. There is no need for ancillary or post-trial care.

Dissemination Plan

The study team plans to disseminate study findings via conference presentation and peer reviewed manuscripts in scientific journals. The study team will also share findings via ClinicalTrials.gov registration. We will follow authorship guidelines depending on the journal to which manuscripts are submitted.

References

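### Should the Day 8 seven-day use items be shortened because Day 1 falls before the first warning?

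*Combined protocol and SAP*

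**What the plan says.** The Outcomes section lists two behavioural secondary outcomes, each a single survey item: "Past 7 day little cigar use (day 8" and "Past 7 day cigarillo use (day 8". The Hypotheses section predicts that pictorial warnings "will decrease LCC susceptibility, past 7 day little cigar use, and past 7 day cigarillo use" relative to both text-only arms.

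Exposure is set out in Methods Overview ("Participants will view a total of 6 different warnings over the course of 6 days") and in Participant timeline ("After the baseline closes, participants will receive a survey every morning for Days 2-7 that includes an LCC warning"). Randomisation comes at the end of the baseline questionnaire, and "The baseline survey will be open to enrollment for 2 days".

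The Sample Size section gives power for willingness only, and adds in general terms that "Secondary outcomes that are measured daily will have higher power to detect differences between groups". The use items are asked once, on Day 8, so neither statement covers them. The available text does not give the items' wording, their response scale, or whether the survey day counts as one of the seven.

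**The concern.** The seven completed days before Day 8 are Days 1 to 7. Six of them follow a warning and one does not. On that reading each use item mixes six days on which the arms can differ with one on which they cannot, and the extra day adds noise without signal.

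These are the only secondary outcomes that measure behaviour. The introduction cites a court ruling that faulted the lack of evidence on smoking rates, so the use items come closest to the gap the study wants to fill. Eligibility also extends to people who may use rarely or never ("Susceptible to using LCCs, or have ever used little cigars and/or cigarillos"), so there is little signal to spare. Matching the recall period to the exposure period looks like a cheap improvement.

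**Working it through.** **Plan's own figure.** Sample Size gives d = 0.26, 233 per group, α = 0.05 and 80% power. A two-sided comparison of two means gives 80.1% (80.0% with the noncentral t), and 233 per arm are needed. The figure reproduces, but it applies to willingness, not to the use items.

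**Which days are in the window.**
- Days 1 to 7: one pre-warning day out of seven. The two-day baseline does not alter this, because Day 2 follows the close of baseline and the day just before it is still the only unexposed day in the window.
- A rolling 168 hours: the overlap depends on clock time. If Day 8 is answered at the same hour as the first Day 2 warning, it is 24 hours; if later in the day, it is shorter. No Day 8 completion time is given.
- Day 8 counted as one of the seven: the window is Days 2 to 8, with no overlap.

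**Day count, Days 1–7 against Days 2–7.** Assume equal daily variance and a common within-person correlation ρ. In units of the daily variance, a sum over L days has variance V(L) = L(1−ρ) + L²ρ. Day 1 adds nothing to the difference between arms, so the standardised effect is multiplied by √(V(6)/V(7)):

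| ρ | V(6) | V(7) | factor |
|---|---|---|---|
| 0 | 6 | 7 | 0.926 |
| 0.2 | 12 | 15.4 | 0.883 |
| 0.5 | 21 | 28 | 0.866 |
| 0.8 | 30 | 40.6 | 0.860 |
| 1 | 36 | 49 | 0.857 |

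Adjusting for baseline use moves the factor towards 0.926. If adjustment removes half of the between-person variance at ρ = 0.5, the variances are 6(0.5) + 36(0.25) = 12 and 7(0.5) + 49(0.25) = 15.75, and the factor is 0.873.

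**Any-use item.** Assume daily use probability p, a 20% cut from Day 2 onward, and 233 per arm. With independent days the risk difference over Days 2–7 is (1−0.8p)⁶ − (1−p)⁶. Adding Day 1 multiplies it by 1−p. At p = 0.10 this is 0.92⁶ − 0.90⁶ = 0.0749, then 0.9 × 0.0749 = 0.0674. The second pair of columns lets p vary between people (beta distribution, intraclass correlation 0.2).

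| p | power, independent days: Days 2–7 | Days 1–7 | power, ICC 0.2: Days 2–7 | Days 1–7 |
|---|---|---|---|---|
| 2% | 12% | 11% | 6.5% | 5.7% |
| 5% | 22% | 19% | 10% | 8% |
| 10% | 37% | 31% | 15% | 12% |
| 20% | 55% | 43% | 23% | 17% |

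These count rejections in the expected direction. Counting both tails gives 7.3% and 6.6% in the lowest ICC row.

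**What adequate power would take.** On the clean Days 2–7 window, 80% power needs daily use to fall by 62%, 43%, 33% or 26% (independent days), or by 81%, 61%, 49% or 40% (ICC 0.2), at the same four use rates. Use rates, cuts and correlations are all assumptions; the documents give none.

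**The case for a change.** The case for a change is that the day count is right on the Days 1–7 reading, that the loss is avoidable, and that it falls on the outcomes nearest to the regulatory question. Borrowing d = 0.26 for illustration, the factor 0.857 gives d = 0.223 and power of 67%; the factor 0.926 gives d = 0.241 and 74%. Asking about the past six days, not counting today, would line recall up with exposure for everyone randomised, and the seven-day item could be kept as a description.

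The day count and the direction of the loss stand. The size is less compelling. The documents attach d = 0.26 to willingness alone. The larger absolute losses in the any-use table need daily use near 20% and independent days. That is hard to expect in a sample that admits people who are merely susceptible, and for a habitual behaviour.

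The remedy also has costs. Data collection methods states a preference for established measures, and a six-day item is unusual. Baseline also asks about tobacco use; if it uses the same seven-day item, a six-day follow-up would break the match. If respondents already count Day 8, the rewording removes no unexposed day. The request to print the item wording is reasonable, but it supplies detail and does not alter the design or analysis.

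**Conclusion.** No change follows. If the window is Days 1 to 7, one unexposed day lowers the standardised effect of a day count to between 0.86 and 0.93 of its Days 2–7 value, assuming a constant daily effect and equal daily variances. If Day 8 is counted, the loss is nil. Day 1 precedes the warnings in all three arms, so the effect is pulled towards zero and neither arm is favoured. The primary outcome is unaffected, and no power claim is undermined.

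A seven-day recall asked at the end of a one-week study is a fair trade-off: a familiar measure, possibly matched to baseline, against a modest and conditional loss. Under the assumed rates and a 20% cut these outcomes have low power on either window, so removing one day would not make a null result informative. The missing wording is a detail the study team can give from the questionnaire when reporting, with a note that the window may include one day before the first warning. The four seven-day items under Other outcomes can be treated the same way.

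### Cognitive elaboration: the day-2 answer is collected after randomization but before any warning, and the plan gives this ready-made baseline no stated role

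*Combined protocol and SAP*

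**What the plan says.** The secondary outcomes in the Outcomes section include "Cognitive elaboration about risk of LCC use (day 8", measured with one item. Daily outcomes are labelled differently, for example "Warning negative affect/worry (each day"; cigar appeal and warning relevance carry the same each-day label. Statistical Methods lets the time of measurement choose the model: "Post-test measures will be analyzed differently than repeated measures from the daily surveys". Post-test measures get a linear or logistic model. Items repeated in the daily surveys get a linear mixed model, with negative affect named as an example.

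Elaboration is also collected daily. Methods Overview says of the surveys on days 2-7: "Before seeing the warning, participants will be asked about how often they have thought about the health risks of smoking cigars". Participant timeline confirms that these surveys contain "questions about their cognitive elaboration over the previous day".

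Randomization takes place at the end of the day-1 survey, and the first warning is shown on day 2. Allocation and Blinding adds: "Participants will not be informed specifically about the possible interventions that they may be assigned to". For day 1 the protocol says: "The baseline survey contains baseline tobacco use and susceptibility questions and additional demographic questions". That description does not name elaboration, although Methods Overview mentions further measures without specifying them.

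**The concern.** The day-2 elaboration answer looks back over the day before the first study warning, and it is given before that warning appears. Participants have been randomized by then but have seen nothing that differs by arm and have not been told what the arms are. The answer is a pre-exposure measurement of the same construct as the listed outcome, and it costs nothing extra. The visible text does not name it as a covariate, as an outcome or as excluded.

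Two things are at stake, both for one hypothesized secondary effect:

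- **Precision.** On a continuous scale, adjusting the day-8 mean difference for a pre-exposure answer leaves the estimated quantity unchanged and reduces its variance.
- **Dilution.** If the daily answers are also analysed, a mixed model written for negative affect would treat day 2 as an ordinary outcome day. That is right for negative affect, which is asked after the warning. It is wrong for elaboration, because no warning can have affected the day-2 answer.

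**Working it through.** **Inputs from the documents (Sample Size):** 233 per arm, d = 0.26 (stated for willingness), alpha 0.05. **Assumptions not in the documents:** two-sided test, continuous elaboration item, the same d = 0.26 for elaboration, and the correlations r shown. SD is set to 1. Power is from the noncentral t distribution.

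**1. The plan's own figure.** Noncentrality = 0.26 × √(233/2) = 2.806, which gives power 80.0%. The stated 80% reproduces. An unadjusted day-8 elaboration contrast with the same d has the same power.

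**2. Day-8 contrast adjusted for day 2.** The variance is multiplied by 1 − r² and one degree of freedom is lost. If a share q answers day 2, missing completely at random, and everyone is kept, the factor is 1 / (q/(1 − r²) + 1 − q). For example, r = 0.5 with q = 0.5 gives 1 / (0.5/0.75 + 0.5) = 0.857.

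| r | Factor, all answer | Power, all answer | Power, 80% answer | Power, 50% answer |
|---|---|---|---|---|
| 0.1 | 0.99 | 80% | 80% | 80% |
| 0.3 | 0.91 | 84% | 83% | 82% |
| 0.5 | 0.75 | 90% | 88% | 86% |
| 0.7 | 0.51 | 98% | 96% | 93% |

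Simulation with 20,000 runs per setting agreed within 0.5 percentage points.

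**3. If the daily answers are also modelled with one arm effect.** Assume equal correlation r between days, all days answered, and a constant effect of 0.26 from day 3 onward.

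- Days 2-7 pooled: effect 0.26 × 5/6 = 0.217, variance (1 + 5r)/6.
- Day 2 dropped: effect 0.26, variance (1 + 4r)/5.
- Day 2 dropped as an outcome and used as covariate: effect 0.26, variance (1 + 4r)/5 − r².

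| r | Days 2-7 pooled | Days 3-7 only | Days 3-7, day 2 as covariate |
|---|---|---|---|
| 0.3 | 95% | 98.8% | over 99% |
| 0.5 | 86% | 95.1% | over 99% |
| 0.7 | 77% | 89.5% | over 99% |

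The middle column isolates the cost of counting day 2 as an outcome. The last column adds the separate benefit of using it as a covariate.

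**The case against.** **The listed outcome already has a model.** A reader might infer that the plan contradicts itself over whether elaboration gets the post-test or the mixed model. The documents do not support that. The each-day label is used consistently for three other measures, elaboration is labelled day 8, and the time-point rule then points to the post-test model. The Sample Size remark, "Secondary outcomes that are measured daily will have higher power to detect differences between groups", is plural although only negative affect among the secondary outcomes is labelled each day. A loose plural there cannot outweigh an explicit label. What stays open is whether the daily elaboration answers are analysed as well, because the mixed-model rule is broad enough to reach them. This objection stands.

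**The visible text may be incomplete.** The Survey timing line in Participant timeline has nothing beneath it, so a table or figure may be lost, and the day-1 survey has unspecified further measures. Elaboration might be asked on day 1. Nor can one infer that it is not asked on day 8, since the post-test description is open-ended. The statement that day 2 has no role is limited to the visible text.

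**The gain is optional and uncertain.** No document gives the correlation. The baseline is open for two days, so the day before day 2 contains the baseline questionnaire for some participants and not for others, which may lower the correlation. At 0.1 nothing is gained. This stands, and it is why the point is a suggestion.

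**The dilution needs several conditions.** It requires the daily answers to be modelled, with a single effect over all days, which the plan does not specify. At correlations of 0.3 and 0.5, pooling still gives more than the 80% of the single day-8 answer; it falls below only at 0.7 (77%).

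**Conclusion.** The point holds as a suggestion to consider for one secondary outcome. The plan collects a pre-exposure elaboration answer on day 2 and, in the visible text, does not use it.

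Adjusting the day-8 contrast for it would raise power by about 4, 10 and 18 percentage points at correlations of 0.3, 0.5 and 0.7 if everyone answers day 2, and by about 2, 6 and 13 points if half do. At 0.1 the gain is negligible. These figures rest on an assumed continuous scale, an effect size borrowed from willingness, and assumed correlations.

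Counting day 2 as an outcome in a daily model would shrink a constant effect by one sixth, but only if such a model with a single arm effect is run.

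It would be wrong to infer that the planned analysis is invalid. The unadjusted day-8 comparison is a sound randomized contrast, and the primary outcome, its analysis and the sample size are untouched.

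**What to change.** - Keep the day-8 between-arm contrast as the listed outcome and state that it is adjusted for the day-2 elaboration answer.
- Use a method that keeps participants who missed day 2, for example a likelihood model for days 2 and 8 with the day-2 arm means constrained equal. This matters because the Compensation Plan requires only three of the six daily surveys, so day-2 answers will be missing for some.
- Say whether the daily elaboration answers are analysed too. If they are, use days 3-7 as outcomes and day 2 as baseline or covariate.

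The cost is a few lines of analysis-plan wording and slightly more analysis work for one secondary outcome. No new data are needed.
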